Repeat of Table 42 for stimulant drug use

Table 56: Summary of Stimulant Drug Use in Past 90 Days by Treatment Arm
Repeat of Table 43 for stimulant drug use

Table 57: Summary of Stimulant Drug Use in Past 180 Days by Treatment Arm
Repeat of Table 49 for stimulant drug use

15 Secondary Outcome Analyses (Patient Level): Marijuana Use

Table 58: Summary Statistics of Marijuana Use by Treatment Arm
Repeat of Table 41 for marijuana use days

Table 59: Summary of Marijuana Use in Past 30 Days by Treatment Arm
Repeat of Table 42 for marijuana use

Table 60: Summary of Marijuana Use in Past 90 Days by Treatment Arm
Repeat of Table 43 for marijuana use

Table 61: Summary of Marijuana Use in Past 180 Days by Treatment Arm
Repeat of Table 49 for marijuana use

16 Secondary Outcome Analyses (Patient Level): Other Drug Use

Table 62: Summary Statistics of Other Drug Use by Treatment Arm

	Treatment Arm		Total (N=)
	EUC (N=)	STOP (N=)	
Monthly Risky Opioid Use (Days)			
3-Month			
N	N		
Mean	X.X		
SD	X.XX		
Minimum	X		
Median	X.X		
Maximum	X		
6-Month			
...			
9-Month			
...			
12-Month			
N	N		
Mean	X.X		
SD	X.XX		
Minimum	X		
Median	X.X		
Maximum	X		

17 Secondary Outcome Analyses (Patient Level): Urine Drug Screen Results

Table 63: Summary of Positive UDS Results by Visit and Treatment Arm
Patient Participants

Visit		Treatment Arm		Total (N=)
		EUC (N=)	STOP (N=)	
Baseline Visit	Number of opioid positive UDS results ¹	n/N (X.X%)		
	Number of opioid + MOUD positive results ²	n/N (X.X%)		
	Number of positive UDS results for any substance	n/N (X.X%)		
	Number of positive UDS results for:			
	Opiates (300 ng)	n/N (X.X%)		
	Oxycodone (100 ng)			
	Methadone (300 ng)			
	Buprenorphine (10 ng)			
	Fentanyl (20 ng)			
	Amphetamine (500 ng)			
	Barbiturate (300 ng)			
	Benzodiazepines (300 ng)			
	Cocaine (150 ng)			
	Ecstasy (500 ng)			
	Methamphetamine (500 ng)			
6-month Visit	...			
	...			
12-month Visit	...			
	...			
	Number of opioid positive UDS results ¹	n/N (X.X%)		
	Number of opioid + MOUD positive results ²	n/N (X.X%)		
	Number of positive UDS results for any substance	n/N (X.X%)		
	Number of positive UDS results for:			
	Opiates (300 ng)	n/N (X.X%)		
	Oxycodone (100 ng)			
	Methadone (300 ng)			
	Buprenorphine (10 ng)			
	Fentanyl (20 ng)			
	Amphetamine (500 ng)			
	Barbiturate (300 ng)			
	Benzodiazepines (300 ng)			

¹ Opioid category includes: opiates (300 ng), oxycodone (100 ng), and fentanyl (20 ng).² Opioid + MOUD category includes: opiates (300 ng), oxycodone (100 ng), methadone (300 ng), buprenorphine (10 ng), and fentanyl (20 ng).

Table 64: Summary of Positive UDS Results by Visit, Prescription for Opioids, and Treatment Arm
Patient Participants

Visit	Prescription for Opioids in Past 6 Months		Treatment Arm		Total (N=)
			EUC (N=)	STOP (N=)	
Baseline Visit	Yes	Number of participants reporting having an opioid prescription in past 6 months on the COMM ¹	N (X.X%)		
		Number of opioid positive UDS results ²	n/N (X.X%)		
		Number of opioid + MOUD positive results ³	n/N (X.X%)		
		Number of positive UDS results for any substance	n/N (X.X%)		
		Number of positive UDS results for:			
		Opiates (300 ng)	n/N (X.X%)		
		Oxycodone (100 ng)			
		Methadone (300 ng)			
		Buprenorphine (10 ng)			
		Fentanyl (20 ng)			
		Amphetamine (500 ng)			
		Barbiturate (300 ng)			
		Benzodiazepines (300 ng)			
		Cocaine (150 ng)			
	No	Ecstasy (500 ng)			
		Methamphetamine (500 ng)			
		Phencyclidine (PCP) (25 ng)			
		Marijuana (50 ng)			
6-month Visit	Yes/No	...			
	Yes/No	...			

¹ Denominator is the number of patient participants.

² Opioid category includes: opiates (300 ng), oxycodone (100 ng), and fentanyl (20 ng).

³ Opioid + MOUD category includes: opiates (300 ng), oxycodone (100 ng), methadone (300 ng), buprenorphine (10 ng), and fentanyl (20 ng).

18 Safety Analyses

Table 65: Summary of Non-fatal Drug or Alcohol Overdose Events in the Past 6 Months, by Treatment Arm

Patient Participants

		Treatment Arm		
Visit		EUC (N=)	STOP (N=)	Total (N=)
Baseline	Number of non-fatal drug or alcohol overdoses	N		
	Number of participants with at least one non-fatal drug or alcohol overdose	N (X.X%)		
	Number of non-fatal drug or alcohol overdoses per participant			
	N	N		
	Mean	X.X		
	SD	XX.X		
	Minimum	X		
	Median	X.X		
	Maximum	X		
6-month	Number of non-fatal drug or alcohol overdoses	N		
	Number of participants with at least one non-fatal drug or alcohol overdose	N (X.X%)		
	Number of non-fatal drug or alcohol overdoses per participant			
	N	N		
	Mean	X.X		
	SD	XX.X		
	Minimum	X		
	Median	X.X		
	Maximum	X		

Table 65: Summary of Non-fatal Drug or Alcohol Overdose Events in the Past 6 Months by Treatment Arm
Patient Participants

		Treatment Arm		
Visit		EUC (N=)	STOP (N=)	Total (N=)
12-month	Number of non-fatal drug or alcohol overdoses	N		
	Number of participants with at least one non-fatal drug or alcohol overdose	N (X.X%)		
	Number of non-fatal drug or alcohol overdoses per participant			
	N	N		
	Mean	X.X		
	SD	X.XX		
	Minimum	X		
	Median	X.X		
	Maximum	X		

Table 66: Summary of Suicide Risk by Treatment Arm Patient Participants			
	Treatment Arm		Total (N=)
	EUC (N=)	STOP (N=)	
Number endorsing suicide risk on PSS ¹ at Baseline	N (X.X%)		
Number endorsing suicide risk on PSS at 6-months	N (X.X%)		
Number endorsing suicide risk on PSS at 12-months	N (X.X%)		
Number endorsing suicide risk on PSS at either 6 or 12-months	N (X.X%)		

¹ Patient Safety Screener. PSS is administered at baseline, 6-months, and 12-months. Endorsing suicide risk on PSS is defined as a response of 'yes' to having thoughts of killing themselves over the last 2 weeks or if they attempted to kill themselves within the last 24 hours (including today) or within the last month (but not today).

Table 67: Summary of Hospitalizations by Treatment Arm				
Patient Participants				
Visit		Treatment Arm		
		EUC (N=)	STOP (N=)	Total (N=)
6-month	Number of hospitalizations	N		
	Numbers of participants with hospitalizations	N (X.X%)		
	Number of hospitalizations per participant			
	0	N (X.X%)		
	1			
	2			
	3			
	4			
	5 or more			
	Number of hospitalizations per participant			
	N	N		
	Mean	X.X		
	SD	X.XX		
	Minimum	X		
	Median	X.X		
	Maximum	X		
12-month	Number of hospitalizations	N		
	Numbers of participants with hospitalizations	N (X.X%)		
	Number of hospitalizations per participant			
	0	N (X.X%)		
	1			
	2			
	3			
	4			
	5 or more			
	Number of hospitalizations per participant			
	N	N		
	Mean	X.X		
	SD	X.XX		
	Minimum	X		
	Median	X.X		
	Maximum	X		

Table 68: Summary of ED Visits by Treatment Arm				
Patient Participants		Treatment Arm		
Visit		EUC (N=)	STOP (N=)	Total (N=)
6-month	Number of ED visits	N		
	Numbers of participants with ED visits	N (X.X%)		
	Number of ED visits per participant			
	0	N (X.X%)		
	1			
	2			
	3			
	4			
	5 or more			
	Number of ED visits per participant			
	N	N		
	Mean	X.X		
	SD	X.XX		
	Minimum	X		
	Median	X.X		
	Maximum	X		
12-month	Number of ED visits	N		
	Numbers of participants with ED visits	N (X.X%)		
	Number of ED visits per participant			
	0	N (X.X%)		
	1			
	2			
	3			
	4			
	5 or more			
	Number of ED visits per participant			
	N	N		
	Mean	X.X		
	SD	X.XX		
	Minimum	X		
	Median	X.X		
	Maximum	X		

Listing 1: Listing of Non-fatal Drug or Alcohol Overdoses by Treatment Arm						
Patient Participants						
Treatment Arm = EUC/STOP						
Site	Participant ID	Date of Enrollment	Visit	Date of Assessment	Number of Overdoses¹	Comments
xxxxxxxxxx	xxxxxxxxxxxxxx	mm/dd/yyyy	Baseline/ 6-month/ 12-month	mm/dd/yyyy	N	xxxxxxxxxx

¹ Only the number of non-fatal drug or alcohol overdoses in the past 6 months are reported at each visit.

Listing 2: Listing of Suicide Risk by Treatment Arm							
Treatment Arm = EUC/STOP							
Site	Participant ID	Date of Enrollment	Visit	Date of Assessment	Over the past 2 weeks, have you had thoughts of killing yourself?	Have you ever attempted to kill yourself?	If yes, when did this last happen?
xxxxxxxxxx	xxxxxxxxxxxxxx	mm/dd/yyyy	Baseline/ 6-month/ 12-month	mm/dd/yyyy	Yes/ No/ Unable to complete	Yes/ No	Within the last 24 hours (including today)/ Within the last month (but not today)/ Between 1 and 6 months ago/ More than 6 months ago

All visits are included for participants who answered 'yes' to having thoughts of killing themselves over the last 2 weeks or if they attempted to kill themselves within the last 24 hours (including today) or within the last month (but not today).

Listing 3: Listing of Hospitalizations by Treatment Arm
Patient Participants

Treatment Arm = EUC/STOP

Site	Participant ID	Treatment Arm = EUC/STOP					Severity	Outcome
		Date of Enrollment	Date of Hospitalization	Date of Discharge	Primary Diagnosis/ Complaint	Secondary Diagnosis/ Complaint	Tertiary Diagnosis/ Complaint	
xxxxxxxxxx	xxxxxxxxxxxx	mm/dd/yyyy	mm/dd/yyyy	mm/dd/yyyy	xxxxxxxxxx	xxxxxxxxxx	xxxxxxxxxx	Recovering/resolving/ Recovered/resolved/ Recovered/recovered with sequela/ Not recovered/not resolved/ Fatal/ Unknown

All hospitalizations are as reported on the ED Visits and Hospitalization (EDH) form.

Listing 4: Listing of ED Visits by Treatment Arm
Patient Participants

Treatment Arm = EUC/STOP						
Site	Participant ID	Date of Enrollment	Date of ED Visit	Date of Discharge	Primary Diagnosis/ Complaint	Secondary Diagnosis/ Complaint
xxxxxxxxxx	xxxxxxxxxxxxxx	mm/dd/yyyy	mm/dd/yyyy	xxxxxx	xxxxxxxxxx	xxxxxxxxxx

All ED visits are as reported on the ED Visits and Hospitalization (EDH) form.

Treatment Arm = EUC/STOP							MedDRA vxx.x	
Site	Participant ID	Date of Enrollment	Date of Death	Source of Death Report	Type	Cause of Death	MedDRA vxx.x	
							Preferred Term	System Organ Class
xxxxxxxxxx	xxxxxxxxxxxx	mm/dd/yyyy	mm/dd/yyyy	Medical chart/ Death certificate/ Autopsy report/ Treating physician/ Other	Primary	xxxxxxxx	xxxxxxxx	xxxxxxxx
					Secondary	xxxxxxxx	xxxxxxxx	xxxxxxxx

19 Data Quality

Table 69: Summary of Data Audits				
Site	Date of Audit	Total Fields Audited¹	Total Data Discrepancies²	Error Rate
Chase-Brexton Health Center	mm/dd/yyyy	N	N	x.xx%
	Subtotal			
Dartmouth-Hitchcock	mm/dd/yyyy			
	Subtotal			
Annville Family Medicine	mm/dd/yyyy			
	Subtotal			
University of Utah	mm/dd/yyyy			
	Subtotal			
The Ohio State University	mm/dd/yyyy			
	Subtotal			
Total	-			

¹ Fields reviewed at monitoring visit comparing the database to source documentation.

² Fields discrepant between database and source documentation.

20 Protocol Deviations

Table 70: Summary of Protocol Deviations by Site

	Chase-Breton Health Center	Dartmouth-Hitchcock	Annville Family Medicine	University of Utah	The Ohio State University	Total
Total number of protocol deviations	N					
Number of protocol deviations related to COVID-19	N (X.X%)					
Number of participants impacted per protocol deviation						
None	N (X.X%)					
One						
More than one						
Total number of major protocol deviations	N					
Number of major protocol deviations related to COVID-19	N (X.X%)					
Type of major protocol deviation						
No consent/assent obtained	N (X.X%)					
Unauthorized assessments and/or procedures conducted prior to obtaining informed consent/assent						
Ineligible participant randomized/inclusion/exclusion criteria not met						
Ineligible participant enrolled/inclusion/exclusion criteria not met						
Stratification error						
Safety event not reported						
Safety event assessment not conducted per protocol						
Breach of confidentiality						
Other significant deviation issues						
Other laboratory assessments issues						
Total number of minor protocol deviations	N					

Table 70: Summary of Protocol Deviations by Site

	Chase-Breton Health Center	Dartmouth-Hitchcock	Annville Family Medicine	University of Utah	The Ohio State University	Total
Number of minor protocol deviations related to COVID-19						
Type of minor protocol deviation	N (X.X%)					
Other informed consent/assent procedures issues	N (X.X%)					
Other inclusion/exclusion criteria issues						
Other laboratory assessments issues						
Study assessments/procedures not followed in accordance with the study protocol						
Inappropriate unblinding						
Other study procedures/assessments issues						
Other randomization procedures issues						
Study behavioral intervention was not provided/performed as per protocol						
Other study behavioral intervention issues						
Safety event reported out of protocol specified reporting timeframe						
Safety event not elicited, observed and/or documented as per protocol						
Other safety event issues						
Destruction of study materials without prior authorization from sponsor						
Other significant deviations issues						

Listing 6: Listing of Protocol Deviations

Deviation Category = XXXXXXXX								
Site	Related Participant IDs	Date of Protocol Deviation	Date Protocol Entered in EDC	Deviation Type	Reason for Protocol Deviation	Related to COVID-19?	Deviation Description	Resolution/ Corrective Action
xxxxxx	xxxxxxxxxxxxxx	mm/dd/yyyy	mm/dd/yyyy	xxxxxx	xxxxxxxx	Yes/No	xxxxxx	Yes/No

Major PDs are Highlighted in grey.

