3.2.7 Primary Outcome Not Available Population

The primary outcome not available population is a subset of the ITT population and consists of the patient participants who missed one or more of the variable(s) used to calculate the primary outcome in the first 6 months of the Healthy Living Monthly Survey (HLM) due to dropout or intermittent missingness. The primary outcome not available population is the complementary set to the primary outcome available population.

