f) If the answer to HMPOSDNY is Yes: (HMPOSDDY) During these 30 DAYS, on how many days did you use your own prescription opioid medications more than prescribed **on the same day** that you used opioid medications that belonged to someone else? (Enter "0" for never)

For all patient participants that reported > 0 days for HMHERFYL **and** > 0 days for (HMPKOTH **or** HMRXMORE **or** HMOPINP):

g) (HMHEROPI) During these 30 DAYS, did you ever use heroin or fentanyl **on the same day** you used prescription opioid medications more than prescribed or that were not prescribed to you (including medications that belonged to someone else)? (y/n)

h) If the answer to HMHEROPI is Yes: (HMHEROOSP) During these 30 DAYS, on how many days did you use heroin or fentanyl **on the same day** you used prescription opioid medications more than prescribed, or that were not prescribed to you (including medications that belonged to someone else)? (Enter "0" for never)

Therefore, the algorithm of generating the days of risky opioid use in the past 30 days to adjust for the days of overlap when different types of risky opioid use occurred on the same day is to:

For patient participants with HMOPIRX=1:

1. Add the items (a) and (b) and subtract (e/f)
2. Add the result from #1 to (d) and subtract (g/h)

For patient participants with HMOPIRX=0:

1. Add the items (c) and (d) and subtract (g/h)

If the calculated days of risky opioid use in the past 30 days is greater than 30 based on the algorithm (e.g., due to the patient participant incorrectly completing the overlap questions), the calculated days of risky opioid use in the past 30 days will be set to 30.

When there are multiple submissions collected for HLM from the same patient participant in the same month, the data from the first submission will be used to calculate the primary outcome. If the data from the first submission is missing, the data in the second submission will be used to calculate the primary outcome. In general, the primary outcome will be calculated from the first collected non-missing data.

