The number and percent of patient participants with the primary outcome data collected in the 6 monthly surveys will be summarized by intervention treatment arm. The primary outcome is considered available for a patient participant if all the questions for risky opioid use (illicit and non-medical) are completed on all six of the monthly surveys. Multiple imputation will be used to impute missing primary outcome data so that there are no missing outcome data in the primary outcome analysis.

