7.2.3 Multiple Imputation for Missingness of the Primary Outcome

The primary outcome, number of days of risky opioid use within the first 180 days since baseline, is measured by repeated monthly assessments. For each monthly assessment, participants will record the number of days of risky use within the previous 30 days. We consider two types of missing data for this outcome:

- *Missingness due to dropout*: patient participants may withdraw early from the study and miss all subsequent monthly measurements.
- *Intermittent missingness*: patient participants may miss one or more monthly surveys, or fail to complete the opioid items on the survey, while remaining enrolled in the study.

It was anticipated during the study design stage that up to 20% of participants may be missing data for the primary endpoint due to dropout and/or nonresponse. Exclusion of those participants with missing values could lead to underestimation of variance and biased estimated parameters. Multiple imputation (MI) will be performed for the primary analysis to account for missingness of the primary outcome variable. For the sake of best practice, if a patient participant misses the response values at baseline and in each of the monthly surveys for the risky opioid use questions for all 12 post-baseline collections, the patient participant will be excluded from multiple imputation since the analysis has little or no information to inform what those actual values might have been.

Multiple imputation consists of three steps:

1. Imputation step. An 'imputation' generally represents one set of plausible values for missing data – multiple imputation represents multiple sets of plausible values. When using multiple imputation, missing values are filled in to generate multiple completed datasets.
2. Completed-data analysis (estimation) step. The desired analysis is performed separately for each dataset that is generated during the imputation step.
3. Pooling step. The results obtained from each completed data analysis are combined into a single multiple imputation result.

Data for the primary outcome analysis is collected from the HLM survey. The analysis dataset includes monthly risky opioid use in Month 1, Month 2, Month 3, ..., Month 6 for the first 6 months post-enrollment, along with baseline risky opioid use, site, treatment, and PCP cluster.

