 - It is assumed that patient participants who drop out will have higher use after their dropout date than those who remain in the study, that is, that days of use after the withdrawal timepoint for dropouts in the treatment arm may more closely resemble that of controls than that of other treated patient participants. The values of missingness due to dropout might not retain the trend of prior observations since they are not exposed in the study environment due to various reasons, therefore the mechanism of missingness is assumed missing not at random (MNAR).

For the imputation of the primary outcome, two separate imputation procedures will be used to complete the imputation process for intermittent missingness and dropout. In the first step, the MI procedure statement uses the Markov Chain Monte Carlo (MCMC) method to impute the values of missing outcomes from intermittent missingness under the missing assumption of MAR. The variables specified in the mixed-effect regression model in Section 7.2.2, are included for imputation of primary outcome. The SAS code for imputing missing data from intermittent missingness is given below.

```
/* imputing the intermittent missingness with MAR assumption */
PROC MI DATA=datamiss nimpute=30 OUT=outimp1 SEED = 100623
min=. . 0 0 0 0 0 0
max=. . 30 30 30 30 30 30;
by treat;
mcmc impute=monotone;
VAR treat site baseline daysinmon1-daysinmon6;
RUN;
```

In this step, this MI procedure produces 30 imputed datasets by filling in the missing values from intermittent missingness with statement “impute=monotone”, and then produces the datasets as monotone missingness. The missing values due to intermittent missingness are imputed assuming that the intervention effect is still carried out while they remain enrolled in the study.

Next, MI procedure is to impute missing values from the dropouts under assumption of missing not at random (MNAR), which is a control-based pattern imputation assuming that after dropout, the unobserved values in the intervention group follow the path of observed values in control group. Based on this assumption, only the observed values in EUC group are used to derive the posterior distribution of the parameters from which the missing values in both EUC and STOP group are imputed. This approach is conservative as it tends to reduce the difference between STOP group and EUC group. The SAS code for imputing missing data from dropout is given below.

```

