Activity	Chase-Brexton Health Center (N=)	Dartmouth-Hitchcock (N=)	Annville Family Medicine (N=)	University of Utah (N=)	The Ohio State University (N=)	Total (N=)
Number of coaching sessions per participant ¹						
No sessions	N (X.X%)					
1 session						
2 sessions						
3 sessions						
4 sessions						
5 sessions						
6 sessions						
Number of coaching sessions per participant						
N	N					
Mean	X.X					
SD	X.XX					
Minimum	X					
Median	X.X					
Maximum	X					

¹ Denominator is the number of STOP patient participants.

8 Primary Outcome Analyses

Table 29: Summary of Primary Outcome Availability by Treatment Arm in ITT Population

Treatment Arm	Number of Participants Enrolled	Number with Primary Outcome Available ¹	Primary Outcome Availability Percentage
EUC	N	N	X.X%
STOP			
Total			

¹ Six monthly surveys contributing to the primary outcome are expected per participant: 1-, 2-, 3-, 4-, 5-, and 6-months post baseline visit. The primary outcome is considered available if all the questions for risky opioid use (illicit and non-medical) are completed on all six of the monthly surveys.

Table 30: Summary of Risky Opioid Use Missing Data Patterns by Treatment Arm in ITT Population

Pattern ¹	HLM Survey							Treatment Arm		Total (N=)
	Baseline	Month 1	Month 2	Month 3	Month 4	Month 5	Month 6	EUC (N=)	STOP (N=)	
1	X	X	X	X	X	X	X	N (X.X%)	N (X.X%)	N (X.X%)
2	X	X	X	X	X	X	O			
3	X	X	X	X	X	O	O			
4	...									
5	X	X	X	X	O	O	X			
6	X	X	O	X	X	X	X			
7	...									
8	O	X	X	O	X	X	O			
9	...									
10	O	O	O	O	O	O	O			

¹A 'X' indicates that risky opioid use was collected at that month on the HLM survey. An 'O' indicates that risky opioid use was not collected at that month on the HLM survey. The different colors indicate 5 missing data patterns and correspond to those in Table 31: No Missing data (blue); Missing due to dropout (orange); Intermittent missing (grey); both intermittent missing and missing due to dropout (green); and all missing (yellow). If a patient participant did not complete the risky opioid use data at baseline and on all 6 of the monthly surveys after baseline, they are categorized in the 'all missing' pattern and the patient participant will be excluded from the primary outcome analysis.

Note: Table provides a representative sample of the missing data patterns that may exist. All patterns seen in the data will be presented at time of final analysis.

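### Imputing only monthly totals ignores the risky-use items answered in a partly completed survey, so an imputed month can fall below days the participant already reported

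*SAP*

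**What the plan says.** - **Availability.** By the Table 29 footnote the outcome is "considered available if all the questions for risky opioid use (illicit and non-medical) are completed on all six of the monthly surveys", and SAP 7.2.1 gives the same rule. SAP 3.2.7 defines the complementary group as those who "missed one or more of the variable(s) used to calculate the primary outcome in the first 6 months", so one missing component variable is enough.
- **Type of missingness.** SAP 7.2.3 includes in intermittent missingness the participants who "fail to complete the opioid items on the survey, while remaining enrolled in the study". Intermittent gaps are imputed under MAR.
- **Monthly total.** SAP 7.2.1 adds the day items: (a) and (b) for those with an opioid prescription, (c) for those without, and (d) heroin or fentanyl for everyone. It then subtracts overlap. Each overlap count (f, h) follows a yes/no gate item (e, g), and the gates are asked only when more than one kind of use was reported that month. If the result exceeds 30, "the calculated days of risky opioid use in the past 30 days will be set to 30". No rule covers a blank item.
- **Imputation.** The variable list in both PROC MI steps is "VAR treat site baseline daysinmon1-daysinmon6". It contains no item-level variable, and no limit depends on the participant's own answers.
- **Repeat submissions.** If the first submission in a month is missing, a later one is used (SAP 7.2.1).

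**The concern.** Taken together, these provisions leave a partly answered month with no total, and the model redraws it as if the participant had said nothing that month. Yet the answers given often fix the total or confine it to a few days. A blank overlap gate or count can arise only after the participant has reported at least two kinds of use, so these are known use months. At stake is the quality of the primary outcome: reported days can be replaced by a value those reports rule out. The same participant also drops out of every analysis without imputation (complete-case, per-protocol, covariate-adjusted and subgroup) because of one blank item in six months.

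**Working it through.** **1. What the answers allow.** The item letters are those of SAP 7.2.1, and the participant's answers are assumed to be mutually consistent. Without a prescription the total is T = c + d − h, and the overlap h cannot exceed the smaller of c and d. So:

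- gate (g) and count (h) both blank: max(c, d) ≤ T ≤ min(30, c + d)
- gate No: h = 0, so T = min(30, c + d)
- gate Yes, count blank: h ≥ 1, so max(c, d) ≤ T ≤ min(30, c + d − 1)

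With a prescription, first form S = a + b − f, then use S in place of c.

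| Answers given | Totals possible | Intended range in the code |
|---|---|---|
| c = 1, d = 2, gate and count blank | 2 or 3 | 0 to 30 |
| c = 1, d = 2, gate No | 1 + 2 = 3 | nothing is missing |
| c = 1, d = 2, gate Yes, count blank | overlap is 1, so 2 | 0 to 30 |
| a = 5, b = 5, f = 5, d = 3, g and h blank | S = 5, so 5 to 8 | 0 to 30 |
| same, gate Yes, count blank | 5 to 7 | 0 to 30 |
| d = 20, c blank | 20 to 30 | 0 to 30 |

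The fourth row shows why answered overlaps must enter the limits: a ceiling equal to the plain sum of day items would be 5 + 5 + 3 = 13.

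**2. The code's limits.** The VAR list has 9 variables, but MIN and MAX have 8 entries each. By position, the 0 and 30 limits fall on baseline and Months 1 to 5, and Month 6 has no entry. Limits of 0 to 30 for all six months are evidently intended. Neither reading gives a floor at reported days.

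**3. Why both steps matter.** The first step fills only the gaps needed to make the pattern monotone. A participant still enrolled who leaves an item blank only in Month 6 already has a monotone pattern. That month therefore passes to the MNAR step, which is fitted on EUC data, although the text assigns item non-response to MAR.

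**4. Blank day item, simulated.** Inputs from SAP 10: 90-day means of 14 and 20, and logit intercept variances of 0.15 (PCP) and 0.25 (individual). Assumed: 30 PCPs of 5 patients per data set; month-level SD of 0, 0.5 or 1; 5% or 20% of participants with a partly answered Month 3; blank item truly zero, so reported days equal the true total. Month 3 was drawn by regression on baseline and the other months, within 0 to 30.

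| Month-level SD | Draws below reported days (5% / 20%) | Mean shift, days (5% / 20%) |
|---|---|---|
| 0 | 46% / 48% | +0.22 / +0.13 |
| 0.5 | 43% / 45% | +0.56 / +0.43 |
| 1 | 40% / 40% | +1.24 / +1.24 |

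**5. Blank overlap gate and count, simulated.** Two simulations used two kinds of use, month variance from 0.1 to 1.0, and prediction from the other five months. Mean use was assumed at 8 to 9 days a month in one, and 9 to 11 days in affected months in the other. Across both, 67% to 84% of draws fell outside the possible range and 25% to 40% fell below reported days. Root-mean-square error was 4.0 to 7.5 days, against 1.6 to 2.3 when draws were held to that range. The second gave a mean shift of about −0.1 to −0.4 days.

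**6. Availability.** If a fraction q of surveys has a blank item, independently across months, the share of participants losing availability is 1 − (1 − q)^6. For assumed q of 1%, 2% and 5% this is 5.9%, 11.4% and 26.5%.

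**The case against.** - **The rule is inferred.** The Table 29 footnote defines availability per participant for a reporting table, and no sentence says how a partly answered month is coded. The Table 32 footnote could be read as item-level imputation. This stands as a caution. But keeping a partial total as observed would conflict with SAP 3.2.7 and 7.2.1, and the code contains no items, so the reading used here is the consistent one.
- **Draws are not free across 0 to 30.** A reader might infer a near-arbitrary redraw. The documents do not support that: draws are conditional on site, baseline and other months, within arm in the first step. The simulations in 4 and 5 condition on other months for this reason, and the mean shift is small.
- **A later submission may fill the gap.** This is true, but only where one exists.
- **The problem will be visible.** SAP 4.2.3 and Tables 22 and 23 count surveys submitted separately from surveys with the risky-use questions completed. That helps, but it does not separate partly answered from wholly blank opioid sections, and it does not change the imputed values.
- **Materiality is not shown.** The blank-item rates are assumed. If the same people skip items repeatedly, fewer participants are affected than 1 − (1 − q)^6 implies. The use levels in the overlap simulations exceed the plan's control range of 10 to 20 days per 90, about 3.3 to 6.7 a month. All of this stands.

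**Conclusion.** The point holds as a weakness in how a stated method uses its data. Followed consistently, the plan ignores answered items in a partly completed month and can impute a total those answers exclude. Within an affected month, a quarter to nearly a half of simulated draws fell below reported days under the stated assumptions. How often such months occur is unknown.

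Stronger readings go too far:

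- A reader might infer a biased rate ratio. The mean shifts are small and differ in sign between set-ups, no difference by arm has been shown, and nothing has been carried through to the 180-day total or to power.
- A reader might infer that any day item of 30 makes the month 30 under the SAP's own rule. That rule has a cap but no floor: inconsistent answers such as 30 + 5 − 10 give 25.
- A reader might infer that a repair returns these participants to the analyses without imputation. It does so only if their outcome becomes complete, which requires each partly answered month to have coinciding limits and no other gap.

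**What to change.** In SAP 7.2.1 and 7.2.3:

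1. For each partly answered month, derive the lowest and highest totals consistent with all answered items, including gates (e, g) and any answered overlap counts (f, h). Gate No means zero overlap; gate Yes with a blank count means an overlap of at least 1. Cap at 30.
2. If a day item is blank, use the total implied by the answered items as the floor and 30 as the ceiling.
3. Where the two limits coincide, set the total and count the month as observed.
4. Otherwise redraw the imputed total within the limits in both the MAR and MNAR steps, before summing to 180 days, or impute at item level. Do not clip draws afterwards, because that piles values at the limits.
5. Flag partly answered months separately in Table 30, reconcile the Table 32 footnote with the code, and align the MIN and MAX lists with VAR.

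The cost is SAP wording and slightly more complex imputation code, with no new data. Participants with a month that stays imputed remain outside the analyses without imputation.
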